### **5.7. Display of Data by Treatment**

All analysis result of Main Study Period excluding ANCOVA will be displayed by the following groups: CT-P10, Rituxan, MabThera, and combined Rituxan and MabThera group.

Analysis of the general and PK section in Main Study Period will be conducted in Part 1 and 2 separately.

All analysis result of Extension Study Period will be displayed by the following groups: CT-P10 maintenance (Group 1), Switched from Rituxan (Group 2), Rituxan maintenance (Group 3), Switched from MabThera (Group 4), and combined Switched from Rituxan and Switched from MabThera group.

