- To assess the additional PK variables of CT-P10, Rituxan and MabThera, during the first course of treatment (over the first 24 weeks).
- To evaluate the pharmacodynamics (PD) and safety of CT-P10, Rituxan and MabThera (over the first 24 weeks).

Part 2

Primary objective:

• To demonstrate that CT-P10 is similar to reference products (Rituxan and MabThera) in terms of efficacy as determined by clinical response according to change from Baseline in disease activity measured by Disease Activity Score using 28 joint counts (DAS28) (C-reactive protein [CRP]) at Week 24.

Secondary objective:

• To evaluate the additional PK (up to Week 48), efficacy, PD, overall safety, and biomarkers of CT-P10 compared with reference products

Sample Size:

Part 1

The first 189 patients will be randomly assigned in a 1:1:1 ratio (approximately 63 patients per treatment group) to the CT-P10, Rituxan and MabThera treatment groups.

Part 2

Approximately 172 subsequent patients will be enrolled in a 1:1 ratio (approximately 86 patients per treatment group) to the CT-P10 or Rituxan treatment groups.

In total, approximately 361 patients will be available for analysis (a total of approximately 149 patients for each of the CT-P10 and Rituxan treatment groups, including up to 63 patients from each CT-P10 and Rituxan treatment group in Part 1, and up to 63 patients from the MabThera treatment group in Part 1).

Main Selection Criteria: Male or female patients with a diagnosis of rheumatoid arthritis (RA) (as defined by the revised 1987 ACR classification criteria) for at least 6 months and active disease (as defined by the presence of 6 or more swollen joints and 6 or more tender joints), and serum C-reactive protein (CRP) \geq 1.5 mg/dL (\geq 15 mg/L) or an erythrocyte sedimentation rate (ESR) \geq 28 mm/hour will be considered for enrollment in the study if they meet all of the inclusion criteria and none of the exclusion criteria.

Inclusion Criteria:

Each patient must meet all of the following criteria to be enrolled in this study:

- 1. Patient is male or female between 18 and 75 years old, inclusive.
- 2. Patient has a diagnosis of RA according to the revised 1987 ACR classification criteria for at least 6 months prior to randomization.
- 3. Patient has active disease as defined by the presence of 6 or more swollen joints (of 66 assessed) and 6 or more tender joints (of 68 assessed), and serum CRP \geq 1.5 mg/dL (\geq 15 mg/L) or an ESR \geq 28 mm/hour.

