2.2 Secondary Objectives

2.2.1 Secondary Objectives: Part 1

The secondary objectives of Part 1 of the study are:

- To assess the additional PK variables of CT-P10, Rituxan and MabThera during the first course of treatment (over the first 24 weeks).
- To evaluate the pharmacodynamics and safety of CT-P10, Rituxan and MabThera (over the first 24 weeks).

2.2.2 Secondary Objective: Part 2

The secondary objective of Part 2 of the study is:

• To evaluate the additional pharmacokinetics (up to Week 48), efficacy, pharmacodynamics, overall safety, and biomarkers of CT-P10 compared with reference products.

3 Investigational Plan

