6.5.10.2 Eliciting and Documenting Adverse Events

Adverse events will be assessed from the date the ICF is signed until the End-of-Study visit.

At every study visit, patients will be asked a standard question to elicit any medically related changes in their well-being. They will also be asked if they have been hospitalized, had any accidents, used any new medications, or changed concomitant medication regimens (both prescription and over-the-counter medications).

In addition to patient observations, AEs will be documented from any data collected on the AE page of the eCRF (e.g., laboratory values, physical examination findings, ECG changes) or other documents that are relevant to patient safety.

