- 17. Additional vital signs including blood pressure, heart and respiratory rates, and temperature (before administration [within 15 minutes prior to the beginning of the study drug infusion], within 15 minutes after the end of the study drug infusion, and at 1 hour (±15 minutes) after the end of the study drug infusion) will be assessed to monitor for possible hypersensitivity reactions. In addition, hypersensitivity should be monitored by routine continuous clinical monitoring including 12-lead ECG monitoring 1 hour (±15 minutes) after the end of the study drug infusion. Emergency equipment, such as adrenaline, antihistamines, corticosteroids, and respiratory support including inhalational therapy, oxygen, and artificial ventilator must be available.
- 18. Pharmacokinetic samples will be collected within 15 minutes prior to the beginning of the study drug infusion, within 15 minutes after the end of study drug infusion, and 1 hour (±15 minutes) after the end of study drug infusion on the day of each study drug infusion. For patients from Part 1, additional samples will be collected after 24 hours (±2 hours) from the start of each study drug infusion in the first treatment course and on Days 7, 21, 28, 56, 84 and 112. Testing will be performed at the central laboratory.
- 19. Pharmacokinetic sampling should be done at EOS Visit if the last visit occurs before Week 48.
- 20. B-cell kinetic samples will be collected in the each treatment course within 15 minutes prior to the beginning of the first study drug infusion, within 15 minutes after the end of first study drug infusion and 1 hour (±15 minutes) after the end of first study drug infusion. For patients from Part 1, additional sample will be collected after 24 hours from the start of the first study drug infusion in the first course of treatment.
- 21. Before dosing on Day 0 of Week 0 (after randomization only). Only for patients who sign a separate informed consent form for the biomarker study (genotypes). Blood samples will be evaluated for FcγR genotype (FcγRIIa, IIIa, and/or any necessary genotypes). Testing will be performed at the central laboratory.
- 22. Use of all concomitant medications, from within 30 days of randomization until the last assessment date or End of Study Visit, will be recorded in the patient's eCRF.

Protocol Version 5.1, including Country-Specific Protocol Amendment 1 (US) - 01 April 2016

Protocol Number CT-P10 3.2

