**Figure 1: Study Schematic**

\* The third course of treatment will be initiated between Week 48 and Week 52 of the Entire Study Period based on the results assessed within 8 weeks from the Extension Week 0.

Any courses of treatment after the first course will be initiated if the following safety criteria are met:

- Absolute neutrophil count should be  $\geq 1.5 \times 10^3$  cells/ $\mu$ L (SI units:  $\geq 1.5 \times 10^9$  cells/L), platelet count should be  $\geq 75 \times 10^3$  cells/ $\mu$ L (SI units:  $\geq 75 \times 10^9$  cells/L), aspartate aminotransferase or alanine aminotransferase should be  $\leq 2.5$  times the upper limit of normal and levels of IgG should be  $\geq 500$  mg/dL (5.0 g/L), at the last blood sample analysis (i.e. Week 16 for second course of treatment and within 8 Weeks from the Extension Week 0 for third course of treatment).
- The patient has not developed any conditions which, in the investigators opinion, would preclude the patient receiving further courses of treatment (e.g., any new or uncontrolled disease such as, but not limited to, cardiovascular disease, or nervous system, pulmonary, renal, hepatic, endocrine, or gastrointestinal disorder).

[figure not shown]
Note that Part 1 and Part 2 of the study will follow the study schematic specified in [Figure 1](#).

In Part 1, the first approximately 189 patients with RA will be randomly assigned in a 1:1:1 ratio to 1 of 3 treatment groups, CT-P10, Rituxan, or MabThera (approximately 63 patients per treatment group).

In Part 2, approximately 172 subsequent patients with RA will be randomly assigned in a 1:1 ratio to 1 of 2 treatment groups, CT-P10 or Rituxan. In total, approximately 361 patients will be available for analysis.

Approximately 189 initial patients to be enrolled in the study will be assigned to Part 1 and all subsequent patients enrolled in the study will be assigned to Part 2. All patients from Part 1 of the study will be included in Part 2 of the study and undergo all assessments performed in Part 2. A schematic of study patient assignment for Part 1 and Part 2 is presented in [Figure 2](#). Part 2 will run independently and in parallel with Part 1.

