### 13. Safety Analyses

The safety analyses will be performed on the safety population and safety – Extension Study Period subset by treatment group presenting data on hypersensitivity monitoring via vital sign measurements (including blood pressure, heart and respiratory rates, and temperature) and electrocardiograms (ECG), immunogenicity tests, vital sign measurements, ECGs, signs and symptoms of tuberculosis (TB), physical examination findings, adverse events (AEs), infections, Infusion-Related Reactions (IRRs), malignancy, clinical laboratory results (hematology, clinical chemistry, urinalysis, and immunoglobulins), and pregnancy tests. Combined PTs using the [APPENDIX 3: Rule of combining Preferred Terms](#) will be summarized in AE tables. Listings will include the PTs as coded without applying the PT combining rule.

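### AE tables pool Parts 1 and 2, so the MabThera column is not like for like with CT-P10 or Rituxan; add Part 1 AE tables over 24 weeks

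*SAP*

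**What the plan says.** **Allocation.** The protocol synopsis (Sample Size) states "The first 189 patients will be randomly assigned in a 1:1:1 ratio (approximately 63 patients per treatment group", to CT-P10, Rituxan and MabThera. After that, SAP 4.1 has "approximately 172 subsequent patients with RA will be randomly assigned in a 1:1 ratio to 1 of 2 treatment groups, CT-P10 or Rituxan". The synopsis gives the pooled size as "a total of approximately 149 patients for each of the CT-P10 and Rituxan treatment groups".

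**Contacts.** Protocol Table 4, footnote 18: "For patients from Part 1, additional samples will be collected after 24 hours (±2 hours) from the start of each study drug infusion". This applies to the first course only, so it means Day 1 and Day 15. Table 7 marks both days as not applicable for Part 2 PK, restricts the Day 1 B-cell sample to Part 1, and schedules no B-cell sample on Day 15.

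**AE enquiry.** Protocol 6.5.10.2: "At every study visit, patients will be asked a standard question to elicit any medically related changes in their well-being".

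**Tabulation.** SAP 5.7 shows Main Study Period results in four columns (CT-P10, Rituxan, MabThera, combined reference) and adds "Analysis of the general and PK section in Main Study Period will be conducted in Part 1 and 2 separately". SAP 13 describes the safety analyses for the safety population and its "Extension Study Period subset by treatment group presenting data on hypersensitivity monitoring via vital sign measurements", with no mention of Part. The list of AE tables in SAP 13.1 is also by treatment group. Where the SAP wants a split it says so: demographics and baseline (7.1, 7.2), medications (9.1), exposure (9.2) and neutralising antibodies (13.7.1) are all by Part. SAP Table 1 lists a safety population under Part 1, but Section 13 assigns no AE table to it.

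**Objective.** Protocol 2.2.1 gives as a Part 1 secondary objective "To evaluate the pharmacodynamics and safety of CT-P10, Rituxan and MabThera (over the first 24 weeks").

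**The concern.** A reader of the AE tables will see CT-P10, Rituxan and MabThera side by side and compare them. Two things differ between the columns besides the product.

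- **Enrolment.** More than half of the CT-P10 and Rituxan patients entered after Part 1 was filled and could not have been allocated to MabThera. That part of the comparison is neither randomised nor concurrent.
- **Opportunity to report.** Part 1 patients have two extra contacts about a day after each first-course infusion. If AEs are asked about there, delayed reactions have a better chance of being recorded in Part 1, and so in the MabThera column.

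The clean comparison, three arms randomised 1:1:1 on one schedule over 24 weeks, is what the Part 1 safety objective calls for. The specified AE tables do not deliver it.

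**Working it through.** **1. The plan's own totals.** Part 1 gives 63 per arm; Part 2 adds 172/2 = 86 each to CT-P10 and Rituxan. CT-P10: 63 + 86 = 149. Reference: 149 + 63 = 212. Total: 149 + 212 = 361. These match the documents.

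**2. Share of each column from Part 1.**

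| Column | From Part 1 | Share *s* |
|---|---|---|
| CT-P10 | 63/149 | 42.3% |
| Rituxan | 63/149 | 42.3% |
| MabThera | 63/63 | 100% |
| Combined reference | 126/212 | 59.4% |

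The remaining 86/149 = 57.7% of CT-P10 and of Rituxan patients come from Part 2.

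**3. Scheduled contacts to Week 24 (Protocol Tables 4 and 7).** Part 1 has 12: Days 0, 1, 7, 14, 15, 21, 28, 56, 84, 112, 140 and 168. Part 2 has the same list without Days 1 and 15, so 10. The mean per column is 10 + 2*s*: 10.85 for CT-P10 and Rituxan, 11.19 for the combined reference, 12.00 for MabThera.

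**4. Size of a possible artefact with identical products.** Let *p* be the rate recorded in Part 1 and *q* the share of those events found only at the extra contacts. A column with Part 1 share *s* then shows *p*[1 − (1 − *s*)*q*]. Hence:

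- CT-P10 minus MabThera = −0.577*pq* (the same for Rituxan minus MabThera)
- CT-P10 minus combined reference = −(0.594 − 0.423)*pq*, or −0.172*pq* from unrounded shares
- CT-P10 minus Rituxan = 0

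For *p*, take the 23% first-infusion reaction rate in Protocol 1.2, as an illustration only. The documents give no value for *q*; the range is an assumption.

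| *q* | CT-P10 | Combined | MabThera | v MabThera (points) | v combined (points) |
|---|---|---|---|---|---|
| 0% | 23.0% | 23.0% | 23.0% | 0 | 0 |
| 5% | 22.3% | 22.5% | 23.0% | −0.7 | −0.2 |
| 10% | 21.7% | 22.1% | 23.0% | −1.3 | −0.4 |
| 20% | 20.3% | 21.1% | 23.0% | −2.7 | −0.8 |
| 30% | 19.0% | 20.2% | 23.0% | −4.0 | −1.2 |

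**5. Sampling error at 23%.** SE = √[0.23 × 0.77 × (1/n₁ + 1/n₂)].

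- Pooled CT-P10 v MabThera (149 v 63): 6.3 points
- Pooled CT-P10 v combined reference (149 v 212): 4.5 points
- Part 1 only, CT-P10 v MabThera (63 v 63): 7.5 points

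At *q* = 30%, root-mean-square error of the pooled MabThera contrast is √(6.32² + 3.98²) ≈ 7.5 points, about equal to the Part 1-only contrast. This counts the artefact in step 4 and not any effect of later enrolment.

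**The case against.** **The reporting mechanism is an inference.** Days 1 and 15 are blood-sampling contacts; no vital signs, examination or safety laboratory test is due. That the AE question is put there follows only from the every-visit rule in Protocol 6.5.10.2. AE monitoring is a continuous row in Table 4, and Protocol 6.5.10.1 tells patients to make contact whenever symptoms develop. Same-day hypersensitivity monitoring (Protocol 6.5.1) and the Day 7 and Day 21 visits are common to both Parts. An event is missed in Part 2 only if it begins after the 1-hour check, is not volunteered, and is not recalled about a week later. This stands: a reader might infer that the tables are biased towards CT-P10, but the documents support only a conditional statement, with zero inside the range.

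**Not all safety output is affected.** Laboratory, vital-sign and ECG schedules are the same in both Parts, so only the enrolment point applies to them. This stands.

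**A Part 1 safety analysis may be intended.** SAP 5.7 requires a split for two sections without forbidding it elsewhere. SAP 5.4 says the listed populations will be analysed, and Part 1 safety is among them. A separate Week 24 report is also planned. A reader might infer that no Part 1 safety analysis is planned at all; that goes too far. But SAP 2 says the document covers all specified analysis, and no AE table in it is assigned to Part 1, so the gap in specification remains.

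**Restricting to Part 1 costs precision.** Step 5 shows that the pooled contrast does no worse even at *q* = 30%, and dropping 86 CT-P10 patients hurts most for uncommon events. This stands against making Part 1 the only basis for MabThera safety statements. It does not count against showing both.

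**Conclusion.** The structural point is confirmed from the documents and needs no assumption: as specified, the AE tables place a MabThera column drawn wholly from Part 1 beside CT-P10 and Rituxan columns that are 42% from Part 1. The combined reference is mildly unbalanced (59% v 42%); CT-P10 versus Rituxan is balanced. The three-arm 24-week safety evaluation named as a Part 1 objective has no specified AE table.

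The effect on the figures is uncertain and probably small. If the extra contacts add reports, CT-P10 would look slightly safer than MabThera: 0 to 4.0 points over the assumed range, and 0 to 1.2 points against the combined reference. Both maxima are below the corresponding standard errors (6.3 and 4.5 points). The effect of later enrolment cannot be sized from the documents. The tables are descriptive, with no safety test or margin planned, so no formal conclusion depends on this. It is a worthwhile, low-cost improvement, not a flaw that undermines the safety assessment.

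**What to change.** In SAP 5.7 and 13:

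1. Add TEAE, SAE, infection and infusion-related-reaction tables for the Part 1 safety population over the first 24 weeks (CT-P10, Rituxan, MabThera, about 63 each), and state that they serve the Part 1 safety objective. If such tables are already intended, say so explicitly.
2. Present them beside the pooled tables wherever CT-P10 or Rituxan is compared with MabThera.
3. Show CT-P10 versus combined reference by Part as well as pooled.
4. Keep the pooled tables, which carry more information on uncommon events.

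The cost is SAP wording and one extra set of tables from data already collected, with no added visits or patients. The Part 1-only contrast is less precise (SE about 7.5 v 6.3 points at a 23% rate), and the text accompanying the tables should say so.

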### **5.8. Missing Values and Outliers**

In order to evaluate the impact of missing data on the efficacy primary endpoint results, additional analyses with missing data imputation will be conducted for the primary efficacy endpoint of DAS28 (CRP) at Week 24 in all-randomized population.

Two imputation methods will be used for sensitivity analysis: Last observation carried forwards (LOCF) and Multiple imputation (MI) with the Missing at random (MAR) assumption. In addition, Tipping point analysis will be conducted based on MI results.

LOCF will impute missing values by the last value observed. MI with the MAR assumption will use regression method to impute missing data. Gender, country (or region), race, baseline value of DAS28 (CRP), prior anti-TNF alpha blocker status (intolerance case versus inadequate response), RF or anti-CCP status (both positive versus both negative versus either RF or anti-CCP negative), study part, treatment group and interaction of treatment group with study part will be used as regression covariates. 10 imputed datasets will be created by multiple imputations, and results from these 10 datasets will be pooled.

LOCF and MI with the MAR results will be provided displaying descriptive statistics for actual value and change from baseline in DAS28 (CRP) at Week 24. Additional, ANCOVA for the DAS 28 (CRP) will be conducted along with its 90% CI between CT-P10 and Reference products treatment group.

Tipping point analyses will be conducted under MNAR (Missing Not at Random) scenarios. Imputed values will be shifted gradually from the imputed values by MI, by treatment groups (CT-P10 versus combined Rituxan and MabThera group) to make MNAR scenarios. A point estimate and 90% confidence interval (CI) for the treatment difference will also be calculated using an analysis of covariance (ANCOVA) considering the treatment as a fixed effect and gender, country (or region), race, study part, interaction of treatment group with study part, prior anti-TNF- $\alpha$  blocker status (intolerance case versus inadequate response), and RF or anti-CCP status (both positive versus both negative versus either RF or anti-CCP negative) fitted as covariates under these scenarios, and the scenario under which confidence interval no longer

rules out differences in the change from baseline of DAS28 (CRP) at Week 24 for the therapeutic equivalence margin of  $\pm 0.5$  will be displayed.

All the MNAR scenarios and corresponding confidence interval will be displayed using three dimensional graph, 2-dimensional contour plot, and table. In the graph, the maximum of absolute value of the lower bound and the upper bound will be used to display CI and corresponding tipping points.

Outliers for the PK primary endpoint parameters will be identified by robust regression method (90% CI) [15]. Details of outliers detected will be presented in the footnotes of the relevant outputs.

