4.2.1 Reasons for Withdrawal

Reasons for withdrawal include the following:

- Patient develops signs of disease progression
- Patient experiences no efficacy from the study drug
- Patient withdraws consent or refuses to continue treatment or procedures/observations
- Patient develops any malignancy
- Patient has any AE that would compromise his or her safety if he or she continues to participate in the study
- Patient has a significant or major protocol violation
- Patient is lost to follow-up
- Patient dies
- Sponsor terminates the study

The investigator will also withdraw a patient upon the request of CELLTRION, Inc. Upon occurrence of a serious or intolerable AE, the principal investigator will confer with the sponsor. Any patient may withdraw his or her consent at any time. CELLTRION, Inc. or its designee may be contacted if clarification is required on a case-by-case basis.

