4.2.2 Handling of Withdrawals

When a patient withdraws from the study, the reason(s) for withdrawal shall be recorded by the investigator on the relevant page of the electronic case report form (eCRF). Whenever possible, all patients who withdraw from the study prematurely will undergo all end-of-study assessments. End-of-study assessments should be completed at least 8 weeks after the last study drug infusion and before study completion. Patients who fail to return for final assessments will be contacted by the study center in an attempt to have them comply with the protocol.

It is vital to obtain follow-up data on any patient withdrawn because of an AE or SAE. In every case, efforts must be made to undertake protocol-specified, safety, follow-up procedures.

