## 6. Patient Disposition

The number of patients who were screened will be displayed. The number and percentage of patients who randomized, initiated, completed, or discontinuing treatment will be displayed using the following categories for all-randomized population and all-randomized population – Extension Study Period subset by treatment group and part.

- Screened
  - Screening Failure
- Randomized
- Initiated first course of treatment in Main Study Period
  - Complete first Course in Main Study Period
  - Discontinued during first Course in Main Study Period
- Initiated second course of treatment in Main Study Period
  - Complete second Course in Main Study Period
  - Discontinued during second Course in Main Study Period
- Initiated treatment in Extension Study Period
  - Complete Extension Study Period
  - Discontinued Extension Study Period

The reasons for screening failure will be displayed using the following categories and ordering:

- Inclusion/Exclusion Criteria Not Met
- Patient Withdrew Consent
- Others

The screening failure summary will include the number of patients out of all screened patients and the primary reason for screening failure. A listing of patients reported as screening failures will also be provided.

The reasons for discontinuation will be displayed using the following categories and ordering:

- Patient develops sign of disease progression
- Patient experiences no efficacy from study drug
- Patient withdraws consent or patient refuses
- Patient develops any malignancy
- Adverse Event
- Significant or major protocol violation
- Lost to follow-up

- Patient died
- Investigator decision
- Sponsor terminates the study
- Pregnancy
- Other

In addition, the treatment duration in days (calculated as date of last visit - date of first infusion in study period + 1) will be calculated and be summarized for patients who discontinue study treatment prematurely. The date of first infusion will be taken as the earliest date recorded on the “Study Treatment Infusion” eCRF page and the date of last visit will be taken as recorded on the “Study Termination” eCRF page.

The disposition listing will list all data collected on the “Study Termination” eCRF along with the date of first infusion for the all-randomized population.

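### The multiple-imputation model in SAP 5.8 uses no DAS28 (CRP) score after baseline, so if patients withdraw after poor interim scores, their imputed Week 24 values and the origin of the tipping-point shifts are too favourable

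*SAP*

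**What the plan says.** SAP 5.8 plans analyses of the all-randomized population to gauge how missing Week 24 DAS28 (CRP) values affect the result: "Two imputation methods will be used for sensitivity analysis", namely LOCF and MI under a missing-at-random (MAR) assumption.

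- **MI.** A regression method with ten imputed data sets. The covariates are gender, country or region, race, baseline DAS28 (CRP), prior anti-TNF status and RF/anti-CCP status, and the list ends: "study part, treatment group and interaction of treatment group with study part will be used as regression covariates". No DAS28 score after baseline appears. Protocol 7.8.5 names MI but no covariates, so it does not fill the gap.
- **LOCF.** "LOCF will impute missing values by the last value observed".
- **Tipping point.** Built on the MI: "Imputed values will be shifted gradually from the imputed values by MI, by treatment groups". On reporting: "All the MNAR scenarios and corresponding confidence interval will be displayed using three dimensional graph, 2-dimensional contour plot, and table".

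The interim scores will exist. The schedules (Protocol 12.1, Table 4; SAP Appendix 1) place a DAS28 examination at Weeks 4, 8, 12, 16 and 20, and at the end-of-study (EOS) visit of patients who withdraw. SAP 11 makes Week 12 DAS28 (CRP) a secondary endpoint.

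Both documents foresee withdrawal for poor response. Protocol 4.2.1 lists "Patient experiences no efficacy from the study drug", and SAP 6 lists "Patient develops sign of disease progression"; each document gives both of these reasons.

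**The concern.** MAR is a statement about the variables in the imputation model. If patients leave because their recent scores were poor, those scores drive the missingness. A model without them imputes an early failure like a completer of the same arm, study part and baseline profile.

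Two outputs then carry the optimism: the imputed Week 24 values, and the point from which the tipping-point shifts are counted. Part of any shift that the result appears to tolerate would only put back information already observed.

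What is at stake is how a sensitivity analysis is read. The primary ANCOVA and the equivalence decision do not use these imputations.

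**Working it through.** **Inputs from the documents** (SAP 5.2 and 5.8; Protocol 7.5): SD 1.32; margin ±0.50; two-sided 90% CI; 149 vs 212 patients enrolled and 133 vs 189 evaluable; drop-out about 10%; ten imputations.

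**Inputs assumed, because the documents give none:** correlation between interim and Week 24 change, the withdrawal mechanism, and the mean course over visits.

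**1. The plan's own figure.** SE = 1.32 × √(1/133 + 1/189) = 0.149. The 90% CI half-width is 1.645 × 0.149 = 0.246. Power at a true difference of 0 is 2Φ(0.50/0.149 − 1.645) − 1 = 0.911, against a stated figure of about 90%. It is reproduced. Planned losses are 361 − 322 = 39, or 10.8%.

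**2. Gap per imputed value, closed form.** Let drop-outs be d SDs worse than their arm at the last interim visit, ρ the correlation of that score with Week 24, and q the drop-out share. Imputing them like completers makes each value too good by ρ·d·SD/(1 − q). With ρ = 0.6, d = 0.5, q = 0.108: 0.6 × 0.5 × 1.32/0.892 = 0.44 points. Over ρ 0.4–0.8 and d 0.5–1.5 the range is 0.3 to 1.8.

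**3. Effect on the treatment difference.** With f the drop-out share and g the gap in each arm (1 = CT-P10), the estimate moves in CT-P10's favour by f₁g₁ − f₂g₂. This is zero when both arms match. When CT-P10 loses more patients, the estimate falls toward 0 if CT-P10 is truly worse, and falls below 0 if the true difference is 0.

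**4. Simulation at a true difference of 0.50.** Six visits with AR(1) correlation; Week 16–Week 24 correlation ρ of 0.6 or 0.8; baseline–change correlation 0 or 0.4 in size; drop-out 5% or 10%. Withdrawal odds rise 2.7-fold per SD of worse latest score, and this drives half or 90% of drop-out. There were 2,000–3,000 trials per setting, with simulation error of about 0.4–0.5 percentage points on a 5% rate. Planned imputations are 0.23–0.48 points too good when half of drop-out is score-driven and 0.42–0.85 when 90% is. The table gives mean difference / rate of declared equivalence for 90% score-driven, baseline correlation 0.4:

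| ρ, drop-out | Full data | Complete case | Planned MI | Sequential MI | LOCF |
|---|---|---|---|---|---|
| 0.6, 5% | 0.497 / 5.1% | 0.487 / 5.9% | 0.490 / 5.7% | 0.498 / 5.1% | 0.515 / 4.1% |
| 0.6, 10% | 0.500 / 4.9% | 0.479 / 7.2% | 0.485 / 6.7% | 0.500 / 5.1% | 0.531 / 3.2% |
| 0.8, 5% | 0.497 / 5.5% | 0.482 / 6.4% | 0.485 / 6.2% | 0.497 / 5.3% | 0.511 / 4.5% |
| 0.8, 10% | 0.501 / 5.6% | 0.472 / 7.8% | 0.478 / 6.9% | 0.500 / 5.0% | 0.524 / 3.9% |

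With baseline correlation 0, in the same row order, planned MI gives 5.6, 6.8, 6.5 and 8.1%, and sequential MI 5.1, 5.0, 6.0 and 5.5%. With half of drop-out score-driven, planned MI gives 4.5–6.0% over all settings, within simulation error of nominal. LOCF values are 0.86–1.28 points too poor.

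**5. Balanced and strongly unequal withdrawal.** With a true difference of 0 in the same model, bias in the difference is at most 0.003, while imputed values stay 0.22–0.68 points too good. A second, simpler simulation (one interim score, all drop-out score-driven, 800 trials, ρ 0.6 and 0.8) imposed the drop-out shares:

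- 10.8% in both arms: arm means 0.08–0.11 too good; difference unbiased to within 0.003.
- True difference 0.50: false equivalence 9–13% at 14.8% vs 8.0% drop-out and 14–17% at 15.8% vs 5.8%; about 4–5% once the interim score is in the model.
- True difference 0, same imbalances: chance of showing equivalence 0.83–0.89, against 0.91–0.93 with the interim score.

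**6. Tipping distance.** Along the CT-P10 axis it is overstated by g₁ − g₂f₂/f₁, for example 0.68 − 0.66 × 0.089/0.119 = 0.19. In step 4 the range is 0.08–0.24.

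**The case against.** The strongest reply is that the point touches little and is partly covered.

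- **Coverage.** LOCF does use interim scores, the shifts are made separately by arm, and all scenarios are displayed, so a reader can find a harsher origin. This stands. But LOCF errs the other way, and Protocol 7.8.5 ties it to missing completely at random. The MI is the only MAR check.
- **Size.** False equivalence rises detectably in step 4 only when 90% of drop-out is score-driven, and no document supports that share: efficacy accounts for two of nine withdrawal reasons in Protocol 4.2.1 and two of twelve in SAP 6. This stands. The 9–17% in step 5 comes from imposed imbalances that the documents do not predict.
- **Comparison.** In every row of the table the planned MI is slightly less optimistic than the complete cases. It is weakly informative; it adds no optimism of its own. This stands.
- **Simulated model.** The simulations left out gender, country, race, anti-TNF status and RF/anti-CCP status. Any prognostic value in these would narrow the gap. This stands as a limit on precision.
- **Tipping distance.** Taking the planned half-width at an observed difference of 0, the result tips at a CT-P10 shift of about (0.50 − 0.246)/0.119 = 2.1 points, so 0.19 is about 9%. At an observed difference of 0.2 it is 0.19/(0.054/0.119), about 42%. The overstatement matters mainly near the margin.

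A reader might infer that the MAR check as a whole leans toward equivalence. The documents do not support that. They list reasons for withdrawal but give no efficacy-related rates by arm, and step 5 shows no bias under balance and the opposite effect when the true difference is 0.

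**Conclusion.** The omission is certain from the text of SAP 5.8. Its consequence is conditional and modest. If some patients withdraw after poor interim scores, the level of the imputed values and the tipping-point origin are too favourable, by about 0.2–0.9 points per imputed value under the graded-withdrawal models.

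The treatment difference is biased only if such withdrawal differs by arm. The bias is toward equivalence when the arm losing more patients is truly worse. It is away from zero, with a lower chance of showing equivalence, when the true difference is 0.

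All sizes rest on assumed correlations, mean course and withdrawal models; only the SD, margin, sample sizes and approximate drop-out come from the documents. Nothing here bears on the primary analysis. This is an optional improvement, worth making because it is cheap.

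**What to change.** In SAP 5.8:

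1. Impute DAS28 (CRP) sequentially, by treatment group, through Weeks 4, 8, 12, 16 and 20 to Week 24. Fill intermittent gaps first, then use monotone regression.
2. Keep the listed baseline covariates and study part, with region in place of country where levels are sparse.
3. Run the MI ANCOVA and the tipping-point analysis from these data sets. Keep LOCF.
4. Use an EOS-visit DAS28 only as an interim predictor, when it falls in a window before Week 24 and is not affected by prohibited RA medication or joint surgery (SAP 11). Do not let it fill the Week 24 value. The limit is needed because Protocol 4.2.2 sets only an early bound, "End-of-study assessments should be completed at least 8 weeks after the last study drug infusion", and the Table 4 footnote allows the visit at any time up to Week 48.

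The cost is SAP wording and a few lines of code, with no new data. The imputation model becomes slightly more complex. Patients with no post-baseline DAS28 gain nothing, since they are still imputed from baseline covariates alone.
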